### **In-depth follow up interview - R100**

**Covid-19 sub-study: participants will be compensated R150 (~\$10) for participating in each study interview.**

## **Uploads**

Upload copy(ies) of unbolded Consent Form(s)

Upload copy(ies) of bolded Consent Form(s)

Upload copy(ies) of unbolded Consent Script(s)

Upload copy(ies) of bolded Consent Script(s)

Upload copy(ies) of recruitment materials/ads to be reviewed

Upload a copy of Certificate of Confidentiality

Upload copy(ies) of the HIPAA form

Upload any additional documents that may be related to this study

citiCompletionCertificate\_11077253\_48182388.pdf

citiCompletionCertificate\_11077253\_48182389.pdf

citiCompletionCertificate\_11077253\_48182390.pdf

## Lay Summary

*This section is intended to provide a basic overview of the study including a description of its purpose, methods, and subject population. The summary should provide a concise overview of the study for non-scientific and scientific members of the IRB. Please avoid medical or technical terminology. In general, the abstract of a grant does not provide a suitable lay summary.*

*Please also paste of a copy of the Lay Summary into the PRISM PSF Form.*

South African adolescent girls and young women (AGYW) remain at extraordinarily high risk of HIV infection. Oral pre-exposure prophylaxis (PrEP) has the potential to alter the epidemic in this vulnerable population, given that it has been shown that if it is adhered to, oral PrEP can protect women from HIV infection. Yet, a critical question is whether AGYW will adopt and adhere to oral PrEP. *Creating demand*—generating interest among at-risk AGYW, who may know little about PrEP and be wary of using it—is critical. There were several barriers that drove non-adherence to PrEP in the VOICE clinical trial. These included low perceived risk, stigma around taking ARVs, mistrust of biomedical products, worries about potential adverse effects, and concerns about partner reactions. These factors may also dampen AGYW’s *uptake* of oral PrEP, but limited attention has focused on *creating demand and motivating uptake*, a gap we aim to address. We propose that two innovations can *reach* young, at-risk AGYW, *inform* them about PrEP and *motivate* them to use it: (1) introducing PrEP through a gender lens in a one-session group workshop; and (2) peer-driven recruitment—recruiting women to attend the workshop by those who have already attended it. To inform intervention development, we will conduct six focus groups with at-risk AGYW (aged 18-25), 10 qualitative interviews with focus group participants, and 20 qualitative interviews with men (10 HIV-positive, 10 HIV-negative or of unknown status) partnered with women in this age range that will explore knowledge of, beliefs about, motivators for, and concerns about using PrEP in the context of gendered relationship dynamics and PrEP-related stigma. Guided by *gender theory* and the *Information Motivation Behavior (IMB)* model, and in collaboration with a Working Group of AGYW, we will develop a virtual (online) group-based Gender-Enhanced (GE) Workshop (using the WhatsApp® platform) to provide PrEP information and address AGYW’s barriers to using it. In a pilot, we will compare AGYW (N=98) randomized to the virtual group-based (GE) workshop (with components that are conducted by participants on

their own time as well as a “real-time” “live” interactive session) or to an Individual Access (IA) condition in which women are given access to a PrEP video and to websites that provide information on PrEP and on contraception options. The primary outcome is having an individual conversation with the study nurse about the possibility of taking up PrEP; secondary outcomes are undergoing HIV-testing and counseling and, if PrEP-eligible, taking up PrEP; and, for all women, *hypothesized mediators* (risk perception, gender barriers, peer norms, self-efficacy, outcome expectancies, PrEP-stigma, attitudes, information) post-intervention and at 3-months. For *Peer-driven recruitment (PDR)* AGYW randomized to either condition will be invited to become *Peer Health Advocates (PHAs)*, who are incentivized to talk to social network members and refer up to three to the workshop type the PHA attended. We will evaluate acceptability and feasibility of PDR by assessing whether the method can be self-sustaining (i.e., on average >50% attendees become PHAs and >2 recruits/PHA attend a workshop); and whether it reaches high-risk women, and women who would not be captured by other methods of recruitment (percent who score high on a new HIV risk tool; percent who never tested or attended family planning). If promising, these approaches will be further tested in a larger study.

Additionally, women who participated in Phase 1 FGs (N = 46) of this study will be invited to participate in a sub-study entitled Sexual and Reproductive Health and Rights of Young Women under the COVID-19 Epidemic (COVID and SRHR). The goal of the sub-study is to understand how the Coronavirus epidemic and related lock-down regulations are affecting young women’s sexual and reproductive health and rights (SRHR) needs and ability to access sexual and reproductive health commodities and services over time (before, during different levels of and after lock-down). Participating women will complete three to four telephone interviews (depending on how long the lock-down lasts) over a one-year period. The interviews will employ mixed methods (quantitative, qualitative and photo-voice). Data collected as part of the sub-study will be combined with the quantitative descriptive data on demographic and sexual and reproductive health characteristics obtained from participating women just prior to the beginning of each FG.

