b. Peer-driven recruitment: (1) Assess acceptability and feasibility of this recruitment method using criteria related to whether the approach could be self-sustaining (i.e., on average  $\geq 50\%$  attendees become PHAs and  $\geq 2$  recruitees/PHA attend a workshop); and (2) Evaluate whether PDR is able to reach women at high-risk (using a new HIV risk tool (10)) and not likely to be captured by other recruitment methods (i.e., percent who never tested or attended family planning).

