Subsequent recruitment. Subsequent PHAs (Waves 2-4) will be drawn from workshop attendees (who do not have to agree to be PHAs), and their numbers will be supplemented if needed using Wave 1 recruitment procedures. At the end of a workshop (or, for IA participants, after viewing the online materials), study staff will invite all participants to become PHAs and to reach out to their network members to help them prevent HIV infection. PHAs will invite network members to participate in the activity (GE or IA) they, themselves, participated in (and will inform them that brief assessments are included). We will repeat this process three more times, for a total of four recruitment “waves” (see Table below). We expect that the initial PHAs (n=16, Wave 1) will refer 28 workshop attendees. Of these 28, we expect at least 50% will agree to be PHAs (Wave 2). These 14 will average two referrals (n=28) who are eligible and participate. We expect half of participants to agree to be PHAs (Wave 3), through a total of four waves. If we fail to enroll 14 new PHAs from the pool of attendees, we will add new recruits, as for the initial seeds. We expect each wave will take approximately two months. To attain a target **98 100** participants attending and completing Waves 2 through 4, we anticipate that we may need to enroll up to 120 women.

Peer-driven recruitment waves and follow-up N = 100 <del>98</del> 100	Wave 1 (seeds)	Wave 2	Wave 3	Wave 4 (if need ed)	
Study Months					
Wave 1: Seeds randomized (1:1) to attend GE or IA condition  Workshop (WS)	16				
Wave 2: Recruitees who participate attend WSs		28 14			
WS Attendees who become PHAs					
Wave 3: Recruitees who participate attend WSs			28 14		
WS attendees who become PHAs					
Wave 4: Recruitees who participate attend WSs				28	
WS Attendees who become PHAs					
Total Attendees/wave (N= 98 <del>100</del> )	16	28	28	28 <del>30</del>	
Follow-up interviews		16	28	28	28

[figure not shown]

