In total, we expect that **98** ~~100~~ women will attend and complete the intervention and assessment activities. To balance recruitment chain size, PHAs will be allowed up to 3 recruitees. PHAs *will not* assess eligibility for workshop attendance, but they will be able to inform potential recruitees of age eligibility, that interactive groups will be audio-recorded, and that the intervention activities are for women *who have had sex*. PHAs will receive R100 (approximately

\$7.69) for each recruitee who is eligible and participates in the activities; they will be told that they will not be paid unless their recruitee is eligible for and completes the activities. To reduce the possibility of coaching, PHAs will be told that staff will confirm criteria; proof of age will be required, and the assessment will ask several questions about sexual activity that may reveal inconsistencies if the recruit was never sexually active. To reduce the possibility of coercion, in the eligibility screener we will ask recruitees how long they have known the PHA who recruited them and if they felt coerced in any way to attend. Any PHA found to be engaging in such behavior will be informed that she may no longer recruit and that she will not get paid for any recruitees who report her as their recruiter.

Procedures for Eligibility screening, informed consent, and study enrollment. Procedures are shown in the

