**Aim 3b.** Peer-driven recruitment: 1) Assess acceptability and feasibility of PDR using pre-specified performance (process) criteria for acceptance and recruitment (on average  $\geq 50\%$  of attendees become PHAs and  $\geq 2$  recruits/PHA attend a workshop); and 2) Evaluate reach of PDR (percent who score high on a new HIV risk tool (10); percent who never tested and never attended family planning. We will estimate these simple proportions from the tracking data and from the pre-workshop assessments.

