3. **Pilot (revised):** To evaluate acceptability, feasibility, and outcomes of the intervention components:
  - a. Intervention: Compare women randomized to the virtual group-interactive workshop with those randomized to individually-accessed links to a PrEP promotional video and PrEP information on the ***primary outcome of having an individual discussion with the study nurse about the possibility of taking up PrEP; undergoing HIV self-testing guided by the study nurse (either in-person at the GHRU office or via telehealth visit) (secondary outcome); if eligible for PrEP, initiating PrEP (secondary outcome),*** and, for all women, changes in hypothesized mediators (information, risk perception, gender barriers, outcome beliefs, PrEP-stigma, peer norms) post-intervention and at 3-month follow-up.
  - b. Peer-driven recruitment: 1) Assess ***acceptability and feasibility*** of peer-driven recruitment (PDR) using pre-specified performance criteria for acceptance and recruitment (on average  $\geq 50\%$  attendees agree to recruit other women (i.e., become Peer Health Advocates [PHAs] and  $\geq 2$  recruits/PHA enroll in the study); and 2) evaluate ***reach*** of PDR (percent who score high on HIV risk assessment; percent who never tested or never attended family planning).

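### Whether peer-driven recruitment sustains itself depends on new attendees per attendee, so the two separate thresholds can class recruitment that replaces itself as not self-sustaining

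*Protocol*

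**What the plan says.** Both copies of the Protocol's lay summary (the online form and the Protocol Summary Form) state the purpose as "We will evaluate acceptability and feasibility of PDR by assessing whether the method can be self-sustaining". They then spell out the meaning as "on average >50% attendees become PHAs and >2 recruits/PHA attend a workshop": two averages, joined by a conjunction, with strict inequalities.

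Protocol, Specific Aims and Hypotheses, Aim 3b, repeats the pair with non-strict inequalities and a looser link: "using criteria related to whether the approach could be self-sustaining".

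The SAP keeps the pair, also non-strict, without the term self-sustaining. Section 3.3.9.3 calls them "pre-specified performance (process) criteria for acceptance and recruitment", and the December 2020 revision says "using pre-specified performance criteria for acceptance and recruitment". The analysis stated for Aim 3b in section 3.3.9.3 is "We will estimate these simple proportions from the tracking data and from the pre-workshop assessments".

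The Pilot Study section gives the planned flow. For the seeds: "We expect that the initial PHAs (n=16, Wave 1) will refer 28 workshop attendees". Half of each later wave is then expected to become PHAs, averaging two attending recruits each. There is a ceiling: "PHAs will be allowed up to 3 recruitees".

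Neither document defines recruits per attendee, or lets a high value on one component offset a low value on the other.

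**The concern.** A recruitment process sustains itself when each attendee brings in, on average, at least one new attendee. That number is the share of attendees who become PHAs multiplied by the attending recruits per PHA. Testing each factor against its own threshold answers a different question. A programme in which many women recruit a little, or fewer women recruit close to the cap, can replace itself and still miss one threshold.

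Peer-driven recruitment is one of the study's two named innovations. Aim 3b could report that it is not self-sustaining while the tracking data show more than one new attendee per attendee.

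**Working it through.** **Identity.** New attendees per attendee, R = (PHAs / attendees) × (attending recruits / PHAs). Recruitment replaces itself when R ≥ 1.

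**Reproducing the plan (Protocol, Pilot Study, wave table).** 28 × 0.50 = 14 PHAs; 14 × 2 = 28 recruits; 16 + 28 + 28 + 28 = 100. The schedule reproduces (98 also appears in the marked-up text).

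**What the thresholds imply.** 0.50 × 2 = 1.00. With non-strict inequalities, meeting both always gives R ≥ 1, so the rule is sufficient for replacement. It is not necessary:

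| PHA share | Recruits per PHA | R | Meets both thresholds? |
|---|---|---|---|
| 70% | 1.6 | 1.12 | No |
| 60% | 1.8 | 1.08 | No |
| 40% | 2.75 | 1.10 | No |
| 60% | 2.2 | 1.32 | Yes |

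With the cap of 3, replacement is possible at any PHA share of at least 1/3. At a 100% share it needs only 1.0 recruit per PHA.

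**The plan judged by its own rule.** Take Waves 1 to 3 as recruiters.
- Seeds counted: PHAs 16 + 14 + 14 = 44; attendees 16 + 28 + 28 = 72; recruits 28 × 3 = 84. Share 44/72 = 61.1%; recruits per PHA 84/44 = 1.91; R = 84/72 = 1.17. Above replacement, but short of 2 per PHA. The seeds alone yield 28/16 = 1.75.
- Seeds excluded: 28/56 = 50%, 56/28 = 2, R = 1.00. This meets the non-strict rule and fails the strict one.

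So if recruitment goes exactly to plan, the result turns on whether seeds count, which is not stated, and on which inequality is used.

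**Size under a model.** The documents give no distribution, so this one is assumed. The 56 attendees of Waves 2 and 3 each become a PHA with probability p. The 16 seeds and those PHAs each hold three independent coupons, redeemed with probability m/3. The share comes from the 56; recruits per PHA include the seeds.

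| True p × m | Both met, ≥ | Both met, > | Observed product ≥ 1 |
|---|---|---|---|
| 70% × 1.6 = 1.12 | under 0.1% | under 0.1% | 83% |
| 60% × 1.8 = 1.08 | about 5% | about 4% | 72% |
| 40% × 2.75 = 1.10 | about 8% | about 5% | 71% |

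With seeds left out of recruits per PHA, the non-strict rule is met in 0.3%, 10% and 8%, and the product exceeds 1 in 79%, 68% and 68%. The pattern does not depend on how seeds are handled.

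**Would a bare product rule do better?** Not by itself. In the same model, a rule that the point estimate exceed 1 passes a true R of 0.96 in about 37% (60% × 1.6) to 40% (40% × 2.4) of pilots, and break-even (50% × 2) in about half. The two-part rule passes those in under 0.1%, 5–8% and 21–30%.

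**The case against.** The two components measure different things, and the aim is acceptability and feasibility as well as sustainability. At 40% × 2.75 most women declined to recruit and the rest came close to the cap; a team may reasonably not call that acceptable. The SAP labels the pair as acceptance and recruitment criteria, the pair is a conservative benchmark, and the product can be worked out from the two reported numbers. All of this stands, and it is a good reason to keep both figures.

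It does not rescue their use as the meaning of self-sustaining, which is how both lay summaries use them.

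The percentages rest on scenarios and a coupon model that are not in the documents. That also stands: they illustrate size. The identity and the plan's own 1.17 need no model, only, for the 1.17, that seeds are counted.

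A reader might infer that missing a threshold means peer-driven recruitment is declared a failure or dropped. The documents do not say so. No consequence of a miss is stated; the lay summary says only that promising approaches will be tested further, and it also weighs reach. Nor does the rule turn away all self-replacing recruitment: 60% × 2.2 meets it.

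**Conclusion.** The point holds as a mismatch between a stated question and its criterion. The two-threshold rule, read with non-strict inequalities, never passes recruitment whose observed product is below 1, but it can class recruitment that replaces itself as not self-sustaining. The plan's own waves do this when seeds are counted (R = 1.17, at 1.91 recruits per PHA). In the assumed model, three self-replacing scenarios meet the non-strict rule in no more than about 8% of pilots, while the observed product reaches 1 in 71% to 83%.

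The consequence is a possible mislabelling of one Aim 3b result in a pilot without a numeric progression rule. The simulated sizes depend on independent coupons and on the chosen scenarios; the direction does not.

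**What to change.** In both copies of the Protocol lay summary, in Protocol Aim 3b, and in the SAP (section 3.3.9.3 and the December 2020 revision of Aim 3b):

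- Define the self-sustaining measure as new attendees per attendee: PHA share × attending recruits per PHA. Compute it from waves whose recruits could still enter the study, and show seeds separately because they are PHAs by requirement.
- Report it with an interval that resamples whole recruitment chains, and interpret that interval against 1. Do not decide on the point estimate alone, given the pass rates at 0.96 and at break-even shown above.
- Keep 50% and 2 per PHA as the acceptance and recruitment targets.
- Use one inequality throughout: the lay summaries are strict, while Aim 3b and the SAP are not. Also settle whether a recruit counts on attending a workshop or, as in the December 2020 text, on enrolling.

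The cost is one ratio from tracking data already collected, plus wording. The drawback is that with few chains the interval will be wide and may be inconclusive.

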## Background, Significance, and Rationale

*In this section, provide a brief summary of the status quo of the relevant work field, and how the proposed study will advance knowledge. Specifically, identify the gaps in knowledge that your project is intended to fill. If no gaps exist that are obviously and directly related to your project, explain how your proposed research will contribute to the overall understanding of your field. Describe potential impacts of your project within your field of study and in a broader context. Provide a critical evaluation of existing knowledge. The literature review does not have to be exhaustive.*

**Despite challenges, biomedical prevention tools have the potential to reduce the extraordinarily high HIV infection risk of young African women; identifying approaches to support effective implementation of oral PrEP to AGYW is therefore a time-sensitive priority.** In South Africa (SA), prevalence among women is 5.6% at ages 15-19 years, increasing to 17.4% at ages 20-24, and 28.4% at ages 25-29 (1). By contrast, prevalence in men is 0.7%, 5.1, and 17.3% in the respective age groups. Trials of ARV-based prevention among women have had mixed results, with some showing a protective effect (2,3) and others not finding such an effect (4-6), especially among younger women (7,8).

*Still, oral PrEP may be the best currently available option for realizing a population-level impact in this vulnerable group (9). First*, although PrEP may have lower bio-activity in the vagina than in the rectum (10), secondary analyses of trial data suggest that when adhered to, oral PrEP is efficacious in women (11,12). **Second**, adherence to (and therefore effectiveness of) PrEP may be higher in open-label than in placebo-controlled trials, as was true in the open-label PROUD study among MSM compared to the placebo-controlled iPrEx trial [86% vs. 44% reduction in risk (13,14)] and HPTN 067, ADAPT-women, an open-label study in SA, where adherence

was 76% in the daily-dosing arm (15). **Finally**, longer-acting methods, which are potentially more effective than those requiring daily dosing, are not yet available. Oral PrEP is a core component of DREAMS (16), and the SA *National Strategic Plan 2017-2022* (17) prioritizes its roll-out to AGYW. Thus, **identifying ways to support effective roll-out is a time-sensitive research priority**.

Yet in implementation and demonstration studies currently underway, considerable attention has been given to identifying effective approaches to ensure high adherence to oral PrEP, but *much less attention to understanding how to present PrEP to AGYW in way that is appealing and will enable them to make informed decisions about whether to use it*. This is a significant gap, as adherence interventions are less appropriate and effective for women who are unsure if PrEP is the right option for them. Without substantial uptake among AGYW at high risk, PrEP's potential to slow incidence among them will be severely limited.

**Even with a known efficacious product, the barriers that drove non-adherence to PrEP in the VOICE trial may dampen AGYW's uptake of oral PrEP.** The qualitative studies of VOICE trial participants, their partners, and community members (VOICE-C; (18,19) revealed that non-adherence (which in some instances was really non-uptake) was driven by *low perception of HIV risk and concerns about partners' reactions*, along with concern about side effects, mistrust of an unproven investigational product, and stigma associated with taking ARV pills. Limited data are available from open-label PrEP studies to evaluate if these are barriers pertain in the context of a known safe and efficacious product. However, women who declined PrEP in CAPRISA 082 (20) cited reasons such as not being ready/willing to take it, concerns about forgetting pills and side effects, not feeling at risk, and belief that family would object; and qualitative data from HPTN 067/ADAPT (21) identified mistrust and stigma as factors influencing persistence with oral PrEP support tools could address some of these barriers, and others might be mitigated by longer-acting PrEP formulations; *but still others—not feeling at risk, stigma concerns, and belief that important persons would not approve—require targeted efforts to change knowledge and underlying beliefs*.

**Gender-related norms for relationships and sexual behavior influence women's use of sexual health promotion methods.** Longstanding research in women's HIV prevention (and contraception) shows the importance to women of their partners' acceptance of their sexual health promotion methods—even those that can be used covertly (22-26)—and this is likely to apply to oral PrEP as well (27,28). Men's views influenced women's participation in the VOICE placebo-controlled trial, as well as their use of study products (29). Relationship dynamics also influenced women's adherence (30) and disclosure (31) to partners in an open-label study of a vaginal gel. Understanding this gendered context is key to engaging women in PrEP use.

**Gender theory serves as the overarching conceptual framework for identifying critical features that affect women's risk, risk perception, and agency.** The above findings around women's concern with male partners' responses are in accord with the Theory of Gender and Power (Gender Theory). Developed by Connell (32), it informs understanding of how gender inequalities in the context of poverty drive the heterosexual HIV epidemics in the US and South Africa, creating vulnerability for men and women (33-36). Whereas men's greater power and norms of *masculinity* shape their behaviors and relations with women (multiple partners, rejection of condom use, acceptance of violence to enforce their prerogatives), women's lesser power and norms of *femininity* shape their response to male power in ways that further enhance their vulnerability (low perceived risk for HIV from stable partners, reluctance to use female condoms or insist on male condoms, and inability to negotiate the terms of sexual relationships, especially if violence is a threat). These relations remain largely intact, despite secular changes in SA granting some women greater economic power, and despite emerging "alternate" masculinities and femininities (34).

Intimate partner violence (IPV), in particular, is strongly associated with young women's increased

vulnerability to HIV acquisition (37, 38, & 39). This is due in part to women's limited agency in relationships characterized by IPV, and to their fear that suggesting condom use or other protective measures will promote abuse. Although oral PrEP may hold promises for women in violent relationships, as it is a method that can potentially be used covertly, use of oral PrEP also holds risks for women. Indeed, data from one PrEP trial have shown that women who experienced any form of partner abuse in the previous three months had lower adherence to PrEP, which they accounted for by stress, distraction, and even partners throwing away pills (40).

This framework gives insight into both the need for oral PrEP—a potentially covert method—in the context of women's lives, and *the potential sources of women's reluctance to use it*. It, thus, helps identify what ideas need to be *brought into consciousness* and challenged in order to create the possibility for women to adopt this critically important HIV prevention method. We propose a gender-enhanced workshop to foster women's understanding that norms for relationships and sexual behavior create risk for women (e.g., that they may be reluctant to use prevention tools that would benefit them if they think their partner may object), and that even if they believe they are acting safely, their loving, single partner can be HIV-infected). Thus, we aim to increase women's *risk perception* in line with community HIV rates and their actual rather than perceived prevention needs. Gender theory ensures that the potential for partner violence is acknowledged, and that women are given tools for avoiding it. Also, by projecting an alternative framework of gender-equality, gender theory can be used to elicit positive motivations for change. Similarly, evidence from contraceptive promotion indicates that giving women choice and a range of options increases overall use, as different products meet the needs of different women (41). Therefore, oral PrEP needs to be offered as one of the options women can use for protection.

**The Information, Motivation, and Behavior (IMB) model directs attention to important proximal factors that underlie behavior change.** The IMB model (42) posits that information, motivational factors, and behavioral skills influence the adoption of a new behavior. Accurate *Information* about PrEP includes its safety and efficacy; knowledge that efficacy is dependent on high adherence; that side effects, if they occur, are short term; and knowledge about why young women are at such high risk of infection. *Motivational Factors* include *positive outcome expectancies*; *negative outcome expectancies* are undesirable consequences. Motivational factors also include *perceived risk*, perceptions of *peer norms*, and *barriers and facilitators*. Based on the findings from VOICE-C, as well as studies of PrEP among men who have sex with men (MSM), *PrEP-related stigma* (50 43) is likely to be among the most important negative outcome expectancies and to be reflected in the norms of social referents. The IMB model also highlights the importance of increasing *Behavioral Skills* and a sense of self-efficacy to adopt PrEP and persist with use despite barriers.

**The premise of the proposed study is that an information/motivation workshop framed through a gender perspective (Women's Sexual Health Options, a Gender-Enhanced Workshop) can increase SA AGYW's interest in PrEP and reduce barriers to considering it.** Theory and experience suggest that framing PrEP as empowering and health enhancing; contextualizing HIV prevention through sexual rights and goals for the future; increasing women's understanding of how gendered relationship dynamics place them at risk; and fostering self-efficacy through practicing how to handle difficult situations can increase willingness to consider oral PrEP and reduce reluctance to adopt it. Based on materials already in use in the SA public sector, the standard of care for PrEP promotion when it is rolled out to AGYW is likely to emphasize information. We thus propose to test if a gender-enhanced PrEP information/motivation workshop can do better than one that only provides information.

**Peer-driven recruitment may be effective in reaching high-risk AGYW to attend the workshops.** In addition to altering social norms, demand-generation requires reaching large numbers of potentially eligible AGYW. *Peer-driven recruitment* (PDR) may be an effective approach for recruiting AGYW to learn about PrEP; we propose to evaluate its feasibility, acceptability, and ability to reach high-risk women, especially those who may not be captured by direct recruitment. AGYW participate in either the Gender-Enhanced WhatsApp group workshop or

individually-accessed weblink information-Only condition can themselves become *Peer Health Advocates* (*PHAs*) who are paid to talk to social network members, give them recruitment materials, and refer them to that workshop type.

The rationale for using chain referral to recruit women draws from sociological theories of group-mediated social control (44), whereby the power of peer influence is harnessed to affect group norms and behaviors (45). This network-based recruitment approach is ideally suited for engaging populations that are not well connected to care (46, 47), which typically is the case for AGYW, many of whom do not attend a family planning clinic until they become pregnant (48). Besides being effective and efficient (49), chain referral may alter group social norms around the target behavior—here, undergoing PrEP clinical assessment. Following on the experience of Bauman (50), PHAs will reach out to their network members and encourage them to attend a sexual health workshop that will be conducted by trained, professional staff. PHAs will be given recruitment materials that include information about PrEP, but will not explicitly invite network members to undergo PrEP clinical assessment, our primary outcome.

**Rationale for the Covid-19 sub-study.** Young women in KwaZulu-Natal are extremely vulnerable to negative sexual and reproductive health and rights (SRHR) outcomes and need to have access to SRHR services and commodities. The recent coronavirus epidemic and its socio-economic responses in the form of a country wide lock-down are likely to affect young women's sexual and reproductive health and rights, exposure to violence and ability to access SRHR services and commodities. In order to better understand the impact of the coronavirus epidemic on young women's SRHR needs and ability to access SRH commodities and SRHR services, this longitudinal sub-study will follow a cohort of young women over time

